8.2.4. Clinical Safety Laboratory Assessments

See [Appendix 2](#) for the list of clinical safety laboratory tests to be performed and the [Schedule of Activities](#) for the timing and frequency. All protocol-required laboratory assessments, as defined in [Appendix 2](#), must be conducted in accordance with the laboratory manual and the [Schedule of Activities](#). Unscheduled clinical laboratory measurements may be obtained at any time during the study to assess any perceived safety issues.

The investigator must review the laboratory report, document this review, and record any clinically relevant changes occurring during the study in the AE section of the CRF. Clinically significant abnormal laboratory findings are those which are not associated with the underlying disease, unless judged by the investigator to be more severe than expected for the participant's condition.

All laboratory tests with values considered clinically significantly abnormal during participation in the study or within **28 calendar days after the last dose of study intervention** should be repeated until the values return to normal or baseline or are no longer considered clinically significant by the investigator or medical monitor.

If such values do not return to normal/baseline within a period of time judged reasonable by the investigator, the etiology should be identified and the sponsor notified.

See [Appendix 6](#) for suggested actions and follow-up assessments in the event of potential drug-induced liver injury.

Participants may undergo random urine drug and cotinine testing at the discretion of the investigator. Drug testing conducted prior to dosing must be negative for participants to receive study intervention.

8.2.5. COVID-19 Specific Assessments

Participants will be tested for SARS-CoV-2 infection by PCR prior to being admitted to the clinic for confinement and subsequent COVID-19 tests will be performed twice weekly while confined to the CRU. Additional testing may be required by local regulations or by the Principal Investigator.

In addition, as per local practices, site-generated COVID-19 Questionnaire will be expected to be completed by the participants each time upon arrival to the clinic – refer to [Schedule of Activities](#).

8.3. Adverse Events and Serious Adverse Events

The definitions of an AE and an SAE can be found in [Appendix 3](#).

AEs will be reported by the participant (or, when appropriate, by a caregiver, surrogate, or the participant's legally authorized representative).

The investigator and any qualified designees are responsible for detecting, documenting, and recording events that meet the definition of an AE or SAE and remain responsible to pursue and obtain adequate information both to determine the outcome and to assess whether the event meets the criteria for classification as an SAE or caused the participant to discontinue the study intervention (see Section [7.1](#)).

Each participant will be questioned about the occurrence of AEs in a nonleading manner.

In addition, the investigator may be requested by Pfizer Safety to obtain specific follow-up information in an expedited fashion.

8.3.1. Time Period and Frequency for Collecting AE and SAE Information

The time period for actively eliciting and collecting AEs and SAEs (“active collection period”) for each participant begins from the time the participant provides informed consent, which is obtained before the participant’s participation in the study (ie, before undergoing any study-related procedure and/or receiving study intervention), through and including a minimum of ***28 calendar days after the last administration of the study intervention.***

Follow-up by the investigator continues throughout and after the active collection period and until the AE or SAE or its sequelae resolve or stabilize at a level acceptable to the investigator and Pfizer concurs with that assessment.

For participants who are screen failures, the active collection period ends when screen failure status is determined.

If the participant withdraws from the study and also withdraws consent for the collection of future information, the active collection period ends when consent is withdrawn.

If a participant definitively discontinues or temporarily discontinues study intervention because of an AE or SAE, the AE or SAE must be recorded on the CRF and the SAE reported using the CT SAE Report Form.

Investigators are not obligated to actively seek AE or SAE after the participant has concluded study participation. However, if the investigator learns of any SAE, including a death, at any time after a participant has completed the study, and he/she considers the event to be reasonably related to the study intervention, the investigator must promptly report the SAE to Pfizer using the CT SAE Report Form.

8.3.1.1. Reporting SAEs to Pfizer Safety

All SAEs occurring in a participant during the active collection period as described in Section 8.3.1 are reported to Pfizer Safety on the CT SAE Report Form immediately upon awareness and under no circumstance should this exceed 24 hours, as indicated in [Appendix 3](#). The investigator will submit any updated SAE data to the sponsor within 24 hours of it being available.

8.3.1.2. Recording Nonserious AEs and SAEs on the CRF

All nonserious AEs and SAEs occurring in a participant during the active collection period, which begins after obtaining informed consent as described in Section 8.3.1, will be recorded on the AE section of the CRF.

The investigator is to record on the CRF all directly observed and all spontaneously reported AEs and SAEs reported by the participant.

8.3.2. Method of Detecting AEs and SAEs

The method of recording, evaluating, and assessing causality of AEs and SAEs and the procedures for completing and transmitting SAE reports are provided in [Appendix 3](#).

Care will be taken not to introduce bias when detecting AEs and/or SAEs. Open-ended and nonleading verbal questioning of the participant is the preferred method to inquire about AE occurrences.

8.3.3. Follow-up of AEs and SAEs

After the initial AE/SAE report, the investigator is required to proactively follow each participant at subsequent visits/contacts. For each event, the investigator must pursue and obtain adequate information until resolution, stabilization, the event is otherwise explained, or the participant is lost to follow-up (as defined in Section 7.3).

In general, follow-up information will include a description of the event in sufficient detail to allow for a complete medical assessment of the case and independent determination of

possible causality. Any information relevant to the event, such as concomitant medications and illnesses, must be provided. In the case of a participant death, a summary of available autopsy findings must be submitted as soon as possible to Pfizer Safety.

Further information on follow-up procedures is given in [Appendix 3](#).

8.3.4. Regulatory Reporting Requirements for SAEs

Prompt notification by the investigator to the sponsor of an SAE is essential so that legal obligations and ethical responsibilities towards the safety of participants and the safety of a study intervention under clinical investigation are met.

The sponsor has a legal responsibility to notify both the local regulatory authority and other regulatory agencies about the safety of a study intervention under clinical investigation. The sponsor will comply with country-specific regulatory requirements relating to safety reporting to the regulatory authority, IRBs/ECs, and investigators.

Investigator safety reports must be prepared for SUSARs according to local regulatory requirements and sponsor policy and forwarded to investigators as necessary.

An investigator who receives SUSARs or other specific safety information (eg, summary or listing of SAEs) from the sponsor will review and then file it along with the SRSD(s) for the study and will notify the IRB/EC, if appropriate according to local requirements.

8.3.5. Exposure During Pregnancy or Breastfeeding, and Occupational Exposure

Exposure to the study intervention under study during pregnancy or breastfeeding and occupational exposure are reportable to Pfizer Safety within 24 hours of investigator awareness.

8.3.5.1. Exposure During Pregnancy

An EDP occurs if:

- A male participant who is receiving or has discontinued study intervention exposes a female partner prior to or around the time of conception.
- A female is found to be pregnant while being exposed or having been exposed to study intervention due to environmental exposure. Below are examples of environmental exposure during pregnancy:
 - A female family member or healthcare provider reports that she is pregnant after having been exposed to the study intervention by ingestion or skin contact while preparing or administering the study drug.

The investigator must report EDP to Pfizer Safety within 24 hours of the investigator's awareness, irrespective of whether an SAE has occurred. The initial information submitted

should include the anticipated date of delivery (see below for information related to termination of pregnancy).

- If EDP occurs in a participant or a participant's partner, the investigator must report this information to Pfizer Safety on the CT SAE Report Form and an EDP Supplemental Form, regardless of whether an SAE has occurred. Details of the pregnancy will be collected after the start of study intervention and until **28 calendar days** after the last dose.
- If EDP occurs in the setting of environmental exposure, the investigator must report information to Pfizer Safety using the CT SAE Report Form and EDP Supplemental Form. Since the exposure information does not pertain to the participant enrolled in the study, the information is not recorded on a CRF; however, a copy of the completed CT SAE Report Form is maintained in the investigator site file.

Follow-up is conducted to obtain general information on the pregnancy and its outcome for all EDP reports with an unknown outcome. The investigator will follow the pregnancy until completion (or until pregnancy termination) and notify Pfizer Safety of the outcome as a follow-up to the initial EDP Supplemental Form. In the case of a live birth, the structural integrity of the neonate can be assessed at the time of birth. In the event of a termination, the reason(s) for termination should be specified and, if clinically possible, the structural integrity of the terminated fetus should be assessed by gross visual inspection (unless preprocedure test findings are conclusive for a congenital anomaly and the findings are reported).

Abnormal pregnancy outcomes are considered SAEs. If the outcome of the pregnancy meets the criteria for an SAE (ie, ectopic pregnancy, spontaneous abortion, intrauterine fetal demise, neonatal death, or congenital anomaly in a live-born baby, a terminated fetus, an intrauterine fetal demise, or a neonatal death), the investigator should follow the procedures for reporting SAEs. Additional information about pregnancy outcomes that are reported to Pfizer Safety as SAEs follows:

- Spontaneous abortion including miscarriage and missed abortion;
- Neonatal deaths that occur within 1 month of birth should be reported, without regard to causality, as SAEs. In addition, infant deaths after 1 month should be reported as SAEs when the investigator assesses the infant death as related or possibly related to exposure to the study intervention.

Additional information regarding the EDP may be requested by the sponsor. Further follow-up of birth outcomes will be handled on a case-by-case basis (eg, follow-up on preterm infants to identify developmental delays). In the case of paternal exposure, the investigator will provide the participant with the Pregnant Partner Release of Information Form to deliver to his partner. The investigator must document in the source documents that the participant was given the Pregnant Partner Release of Information Form to provide to his partner.

8.3.5.2. Exposure During Breastfeeding

An exposure during breastfeeding occurs if:

- A female is found to be breastfeeding while being exposed or having been exposed to study intervention (ie, environmental exposure). An example of environmental exposure during breastfeeding is a female family member or healthcare provider who reports that she is breastfeeding after having been exposed to the study intervention by inhalation or skin contact.

The investigator must report exposure during breastfeeding to Pfizer Safety within 24 hours of the investigator's awareness, irrespective of whether an SAE has occurred. The information must be reported using the CT SAE Report Form. When exposure during breastfeeding occurs in the setting of environmental exposure, the exposure information does not pertain to the participant enrolled in the study, so the information is not recorded on a CRF. However, a copy of the completed CT SAE Report Form is maintained in the investigator site file.

An exposure during breastfeeding report is not created when a Pfizer drug specifically approved for use in breastfeeding women (eg, vitamins) is administered in accord with authorized use. However, if the infant experiences an SAE associated with such a drug, the SAE is reported together with the exposure during breastfeeding.

8.3.5.3. Occupational Exposure

An occupational exposure occurs when a person receives unplanned direct contact with the study intervention, which may or may not lead to the occurrence of an AE. Such persons may include healthcare providers, family members, and other roles that are involved in the trial participant's care.

The investigator must report occupational exposure to Pfizer Safety within 24 hours of the investigator's awareness regardless of whether there is an associated SAE. The information must be reported using the CT SAE Report Form. Since the information does not pertain to a participant enrolled in the study, the information is not recorded on a CRF; however, a copy of the completed CT SAE Report Form is maintained in the investigator site file.

8.3.6. Cardiovascular and Death Events

Not Applicable.

8.3.7. Disease-Related Events and/or Disease-Related Outcomes Not Qualifying as AEs or SAEs

Not Applicable.

8.3.8. Adverse Events of Special Interest

Not Applicable.

8.3.8.1. Lack of Efficacy

This section is not applicable because efficacy is not expected in the study population.

8.3.9. Medical Device Deficiencies

Not Applicable.

8.3.10. Medication Errors

Medication errors may result from the administration or consumption of the study intervention by the wrong participant, or at the wrong time, or at the wrong dosage strength.

Exposures to the study intervention under study may occur in clinical trial settings, such as medication errors.

Safety Event	Recorded on the CRF	Reported on the CT SAE Report Form to Pfizer Safety Within 24 Hours of Awareness
Medication errors	All (regardless of whether associated with an AE)	Only if associated with an SAE

Medication errors include:

- Medication errors involving participant exposure to the study intervention;
- Potential medication errors or uses outside of what is foreseen in the protocol that do or do not involve the study participant.

Such medication errors occurring to a study participant are to be captured on the medication error page of the CRF, which is a specific version of the AE page.

In the event of a medication dosing error, the sponsor should be notified within 24 hours.

Whether or not the medication error is accompanied by an AE, as determined by the investigator, the medication error is recorded on the medication error page of the CRF and, if applicable, any associated AE(s), serious and nonserious, are recorded on the AE page of the CRF.

Medication errors should be reported to Pfizer Safety within 24 hours on a CT SAE Report Form **only when associated with an SAE**.

8.4. Treatment of Overdose

For this study, any dose of PF-06865571 greater than 1800 mg within a 24-hour time period will be considered an overdose.

Sponsor does not recommend specific treatment for an overdose.

In the event of an overdose, the investigator should:

1. Contact the medical monitor within 24 hours.
2. Closely monitor the participant for any AEs/SAEs and laboratory abnormalities for at least 5 half-lives or 28 calendar days after the overdose of PF-06865571 (whichever is longer).
3. Document the quantity of the excess dose as well as the duration of the overdose in the CRF.
4. Overdose is reportable to Safety **only when associated with an SAE**.
5. Obtain a blood sample for PK analysis **as soon as possible** upon identification of overdose.

Decisions regarding dose interruptions or modifications will be made by the investigator in consultation with the medical monitor based on the clinical evaluation of the participant.

8.5. Pharmacokinetics

The samples collected for PK (PF-06865571 concentration), radioactivity (total ^{14}C) and/or metabolite profiling assessment must be processed and shipped as indicated in the instructions provided to the investigator site to maintain sample integrity. Any deviations from the sample handling procedure (eg, sample collection and processing steps, interim storage or shipping conditions), including any actions taken, must be documented and reported to the sponsor. On a case-by-case basis, the sponsor may make a determination as to whether sample integrity has been compromised.

Samples collected for PK, radioactivity and/or metabolite profiling/ID may also be used to evaluate safety or efficacy aspects related to concerns arising during or after the study, for metabolite identification and/or evaluation of the bioanalytical method, or for other internal exploratory purposes.

Genetic analyses will not be performed on these samples unless consent for this was included in the informed consent. Participant confidentiality will be maintained.

8.5.1. Period 1 Plasma for Analysis of Total ^{14}C and Metabolite Profiling/ID

During **Period 1**, blood samples of approximately 4 mL for total ^{14}C and 10 mL for metabolite profiling/ID, to provide approximately 1.6 mL and 4 mL of plasma, respectively, will be collected into appropriately labeled tubes containing K₂EDTA at times specified in the **Schedule of Activities**. Instructions for the collection and handling of biological samples will be provided in the laboratory manual or by the sponsor. The actual date and time (24-hour clock time) of each sample will be recorded.

The actual times may change, but the number of samples will remain the same. All efforts will be made to obtain the samples at the exact nominal time relative to dosing. Collection of samples up to and including 10 hours after dose administration that are obtained within 10% of the nominal time relative to dosing (eg, within 6 minutes of a 60-minute sample) will not be captured as a protocol deviation, as long as the exact time of the collection is noted on the source document and the CRF. Collection of samples more than 10 hours after dose administration that are obtained \leq 1 hour away from the nominal time relative to dosing will not be captured as a protocol deviation, as long as the exact time of the collection is noted on the source document and the CRF. This protocol deviation window does not apply to samples to be collected more than 10 hours after dose administration at outpatient/follow-up visits with visit windows.

Details regarding the collection, processing, storage and shipping of the blood samples will be provided in the lab manual.

8.5.2. Period 2 Plasma for Analysis of [¹⁴C]PF-06865571 (After IV Administration)

During **Period 2**, blood samples of approximately 4 mL, to provide approximately 1.6 mL of plasma, for PK analysis of radiolabeled [¹⁴C]PF-06865571 will be collected into appropriately labeled tubes containing K₂EDTA at times specified in the [Schedule of Activities](#). Instructions for the collection and handling of biological samples will be provided in the laboratory manual or by the sponsor. The actual date and time (24-hour clock time) of each sample will be recorded.

The actual times may change, but the number of samples will remain the same. All efforts will be made to obtain the samples at the exact nominal time relative to dosing. Collection of samples up to and including 10 hours after dose administration that are obtained within 10% of the nominal time relative to dosing (eg, within 6 minutes of a 60-minute sample) will not be captured as a protocol deviation, as long as the exact time of the collection is noted on the source document and the CRF. Collection of samples more than 10 hours after dose administration that are obtained \leq 1 hour away from the nominal time relative to dosing will not be captured as a protocol deviation, as long as the exact time of the collection is noted on the source document and the CRF. This protocol deviation window does not apply to samples to be collected more than 10 hours after dose administration at outpatient/follow-up visits with visit windows.

Windows defined for times relative to oral dosing are intended to ensure accurate sample collection as required for the analysis of both oral and IV data.

Details regarding the collection, processing, storage and shipping of the blood samples will be provided in the lab manual.

Samples collected for measurement of plasma radiolabeled [¹⁴C]PF-06865571 concentrations will be analyzed using a validated quantitative AMS method after chromatographic separation of the parent compound in compliance with applicable SOPs.

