Total Radioactivity ^q (P2 Only)							X	→	→	→	→	→	→	→	→	→	X	→	→	X	→	→	X ^q				
Feces Sample collection for -																											
Total Radioactivity and Metabolite ID ^r (P1 Only)		X ^r	X	→	→	→	→	→	→	→	→	→	→	→	→	→	→	X	→	→	X	→	X	X	X	X ^r	X
[¹⁴ C]PF-06865571 ^r (P2 Only)							X ^r	→	→	→	→	→	→	→	→	→	→	→	→	→	→	X	→	→	X ^r		

Abbreviations: →= ongoing/continuous event; AE = adverse event; COVID-19 = Coronavirus disease 2019; CRU = Clinical Research Unit; ECG = electrocardiogram; ET=early termination; F/U=follow-up; HCVAb = hepatitis C antibody; HBsAg = hepatitis B surface antigen; HIV = human immunodeficiency virus; P1 = Period 1; P2 = Period 2; PK = pharmacokinetics; SAE = serious adverse event; LC/MS = liquid chromatography tandem mass spectrometry; ET = early termination.

Visit Identifier	Screening	Period 1 (P1) and Period 2 (P2), unless otherwise limited to 1 of these 2 Periods ^a																					F/U Phone Call	ET	
Days Relative to Day 1	-42 to -2	-1																							
Hours After Oral PF-06865571 Dose	-	-	0	0.5	1	2	3	3.08	3.17	3.25	3.5	3.75	4	6	9	12	16	24	27	36	48	51	72	96	120
Hours After IV [¹⁴ C]PF-06865571 Dose (P2 Only)			-3				0	0.08 3 (5 min)	0.17 (10 min)	0.25 (15 min)	0.5 (30 min)	0.75 (45 min)	1	3	6	9	13	21	24	33	45	48			

Note: Black color denotes oral dose administration and sampling post oral administration and Red color denotes IV dose administration and sampling post IV administration. IV samples may optionally be labeled with the corresponding time relative to the oral dose for sample collection; however, PK data for the IV administration will be analyzed relative to the start of the IV infusion.

- There will be a wash-out period of 8-22 days from drug administration in Period 1 and Period 2. The day to start Period 2 is dependent on the duration for Period 1 but will be at least after all sample collection in Period 1 are complete.
- In Period 2, participants will be discharged on Day 3 (ie, 48 hours IV dose administration).
- Dosing in Period 2 (as 1 cohort) or Completion of Period 1 (1 participant at a time) when at least 1 of 3 criteria are met: (1) ≥90% of radioactive dose has been recovered in urine+feces+emesis (if any); (2) <1% of radioactive dose has been recovered in urine+feces during 24H interval over 2 consecutive days; (3) participant has reached Day 21 (in Period 1). At the latest, Period 2, Day -1 would occur on the same day as Period 1, Day 21.

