4. STUDY DESIGN

4.1. Overall Design

This study is a Phase 1, open-label, non-randomized, 2-period, fixed-sequence, single-dose study of PF-06865571 in healthy male participants to characterize the ADME properties of [¹⁴C]PF-06865571 following oral administration; and to evaluate the absolute oral bioavailability (F) and fraction absorbed (Fa) of PF-06865571 following oral administration of unlabeled PF-06865571 and IV administration of [¹⁴C]PF-06865571.

In this study 6 participants will be enrolled to ensure evaluable data is acquired in at least 4 participants. Each participant will receive 2 regimens (A and B) in Periods 1 and 2, respectively, as outlined in Figure 1. Participants who withdraw from the study may be replaced if the number of evaluable participants is less than 4.

Figure 1. Two (2)-Period Fixed Sequence Study Design

* Completion of Period 1 (1 participant at a time) when at least 1 of 3 criteria are met: (1) $\geq 90\%$ of radioactive dose has been recovered in urine+feces+emesis (if any); (2) $< 1\%$ of radioactive dose has been recovered in urine+feces during 24H interval over 2 consecutive days; (3) participant has reached Day 21 (in Period 1). At the latest, Period 2, Day -1 would occur on the same day as Period 1, Day 21.

Regimen A in Period 1: An oral dose of 300 mg PF-06865571 containing approximately 300 nCi ^{14}C (ie, radiolabeled PF-06865571) will be administered within approximately 10 minutes of completion of a standard breakfast (see Sections 5.3.1 and 6.1.1).

Regimen B in Period 2: An oral dose of 300 mg unlabeled PF-06865571 followed at T_{max} by an IV dose of 300 nCi $[^{14}\text{C}]$ in 100 μg of PF-06865571 (3 $\mu\text{Ci}/\text{mg}$ active drug). The $[^{14}\text{C}]$ IV dose will be administered as an infusion over approximately 15 minutes. Oral unlabeled PF-06865571 will be administered within approximately 10 minutes of completion of a standard breakfast (see Sections 5.3.1 and 6.1.1).

Screening will occur within 42 days of the first dose of the investigational product in Period 1. All participants will provide informed consent and undergo screening evaluations to determine their eligibility.

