6.1.1. Administration

In Period 1, [¹⁴C]PF-06865571 will be administered as an oral dose. In Period 2, the oral unlabeled PF-06865571 will be administered 3 hours before the IV [¹⁴C]PF-06865571 dose.

¹⁴C labeled or unlabeled PF-06865571 (300 mg): A standard meal will be provided approximately 30 minutes prior to oral PF-06865571 administration in each period. The breakfast will be consumed over approximately a 20-minute interval. Participants will be encouraged to complete the entire breakfast. Qualified investigator site personnel will administer labeled or unlabeled PF-06865571 via oral route at approximately 0800 hours (plus or minus 2 hours) within approximately 10 minutes of completion of the meal during the designated period with water to a total volume of 240 mL according to the site administration instructions.

¹⁴C]PF-06865571 (100 µg): Ten mL of the 10 µg/mL manufactured IV solution of [¹⁴C]PF-06865571 will be administered intravenously (over 15 minutes as a continuous infusion through an infusion line using a calibrated syringe pump or similar). Preparation and administration of [¹⁴C]PF-06865571 will be performed by qualified investigator site personnel (in accordance with local regulations and laws). Further details on administration are outlined in the site administration instructions.

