9.4.2. Secondary Endpoint(s)

9.4.2.1. Pharmacokinetic Parameters

9.4.2.1.1. Plasma

The PF-06865571 PK parameters following a single dose administration of unlabeled PF-06865571 (oral) and microtracer dose of [¹⁴C]PF-06865571 (oral and IV) will be derived, where appropriate, from the concentration-time profiles as outlined below:

- Parameters for total ¹⁴C (¹⁴C oral microtracer) will be derived for Period 1 only;
- Parameters for PF-06865571 after oral doses of ¹⁴C oral microtracer and unlabeled PF-06865571 for Periods 1 and 2, respectively and for [¹⁴C]PF-06865571 after ¹⁴C IV microtracer for Period 2 will be derived.

Parameter	Definition	Method of Determination
AUC _{last}	Area under the plasma concentration-time profile from time zero to time of the last quantifiable concentration (C _{last})	Linear/Log trapezoidal rule
AUC _{last(dn)}	Dose normalized AUC _{last}	AUC _{last} /Dose
AUC _{inf^a}	Area under the plasma concentration-time profile from time zero extrapolated to infinite time	AUC _{last} + (C _{last} * / k _{el}), where C _{last} * is the predicted plasma concentration at the last quantifiable time point estimated from the log-linear regression analysis
AUC _{inf(dn)^a}	Dose normalized area under the plasma concentration-time profile from time zero extrapolated to infinite time	AUC _{inf} /Dose

Parameter	Definition	Method of Determination
C_{\max}	Maximum plasma concentration	Observed directly from data
$C_{\max}(\text{dn})$	Dose normalized maximum plasma concentration.	C_{\max}/Dose
T_{\max}	Time for C_{\max}	Observed directly from data as time of first occurrence
$t_{1/2}^a$	Terminal elimination half-life	$\text{Log}_e(2)/k_{\text{el}}$, where k_{el} is the terminal phase rate constant calculated by a linear regression of the loglinear concentration time curve. Only those data points judged to describe the terminal loglinear decline will be used in the regression
CL/F^a (oral)	Apparent clearance following oral administration	$\text{Dose}/\text{AUC}_{\text{inf}}$
CL^a (IV)	Systemic clearance	$\text{Dose}/\text{AUC}_{\text{inf}}$
V_z/F^a (oral)	Apparent volume of distribution following oral administration	$\text{Dose}/(\text{AUC}_{\text{inf}} * k_{\text{el}})$
V_{ss}^a (IV)	Steady-state volume of distribution following IV infusion	$V_{ss} = \text{CL} \times [\text{MRT} - (\text{infusion time}/2)]$ where MRT is the Mean Residence Time and is calculated as $\text{AUMC}_{\text{inf}}/\text{AUC}_{\text{inf}}$

a. If data permit.

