6.3. Secondary Endpoints

- *Period 1: AUC_{last}, C_{max}, T_{max}, and if data permit, AUC_{inf} and t_{1/2} to describe single oral dose of:*
 - *Total radioactivity in plasma;*
 - *PF-06865571 in plasma.*
- *[¹⁴C]PF-06865571 (Period 2): AUC_{last}, C_{max}, T_{max}, and if data permit, t_{1/2}, AUC_{inf}, CL and V_{ss}.*
- *Plasma AUC_{inf} of oral unlabeled PF-06865571 and IV microtracer of [¹⁴C] PF-06865571 in Period 2 only.*
- *Total urinary radioactivity following oral administration of [¹⁴C] PF-06865571 in Period 1 and IV microtracer administration of [¹⁴C] PF-06865571 in Period 2.*

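### Does the unnamed dosing clock in Protocol 8.5.2 put the early IV [14C] samples, and so IV Cmax and Tmax, at risk?

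*Protocol*

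**What the plan says.** Protocol 8.5.2 covers Period 2 blood draws for IV [14C]PF-06865571. Up to 10 hours, a sample is not a deviation if it is "obtained within 10% of the nominal time relative to dosing (eg, within 6 minutes of a 60-minute sample"), provided the exact time is noted. Beyond 10 hours the allowance is 1 hour. The stated target is tighter: "All efforts will be made to obtain the samples at the exact nominal time relative to dosing".

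Sections 8.5.1 and 8.5.3 give the same window rule. Only 8.5.2 adds a further sentence: "Windows defined for times relative to oral dosing are intended to ensure accurate sample collection", for the analysis of oral and IV data alike.

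Period 2 has two doses. Under Protocol 6.1.1, "the oral unlabeled PF-06865571 will be administered 3 hours before the IV" dose. Protocol 4.1 says the "IV dose will be administered as an infusion over approximately 15 minutes". The note to the Schedule of Activities (Protocol 1.3) says "IV samples may optionally be labeled with the corresponding time relative to the oral dose for sample collection", and it fixes the start of infusion as time zero for analysing IV data.

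IV Cmax and Tmax are secondary endpoints (Protocol 3, SAP 6.3). Under Protocol 9.4.2.1.1, Cmax is read straight from the data, and Tmax is "Observed directly from data as time of first occurrence".

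**The concern.** The rule refers to dosing without saying which dose, and the extra sentence in 8.5.2 mentions oral dosing. If a site took that sentence to set the window, the tolerance for an early IV sample would be 10% of more than 3 hours instead of 10% of a few minutes. A draw made before the infusion began could then pass as an on-time 5, 10 or 15 minute sample.

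This would matter most for IV Cmax and Tmax. With a 15-minute infusion the peak falls at the end of infusion, and a peak that was not sampled cannot be recovered by using actual times or by excluding the mistimed value. Concentration summaries and median plots, which the SAP bases on nominal times, would also be blurred.

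**Working it through.** **1. The protocol's own example.** 0.10 × 60 min = 6 min, as 8.5.2 states.

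**2. Windows on each clock.** Oral time = IV time + 180 min. Window = 0.10 × nominal time.

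| IV nominal (min) | Oral nominal (min) | Oral-clock window | IV-clock window |
|---|---|---|---|
| 5 | 185 | ±18.5 | ±0.5 |
| 10 | 190 | ±19.0 | ±1.0 |
| 15 | 195 | ±19.5 | ±1.5 |
| 30 | 210 | ±21.0 | ±3.0 |
| 45 | 225 | ±22.5 | ±4.5 |
| 60 | 240 | ±24.0 | ±6.0 |

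Measured from infusion start, the first three oral-clock windows run from −13.5 to 23.5, −9 to 29 and −4.5 to 34.5 min. All three begin before the infusion and end after it, and they share the span −4.5 to 23.5 min.

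**3. Which clock the text supports.** The heading of 8.5.2 limits the section to samples after IV administration. The Schedule of Activities gives these samples IV nominal times and makes the oral label optional. The 60-minute example fits the IV clock, which has a 60-minute sample. The added sentence states a purpose, accurate collection, which an oral-clock window would defeat for a 5-minute sample. It does make sense for later draws at time points shared with unlabeled drug. At IV 3, 6 and 9 h (oral 6, 9 and 12 h), the two clocks give 36 against 18, 54 against 36 and 60 against 54 min, so the two are of similar order. The IV clock is the better reading for the early samples.

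**4. Whether the window reaches the data.** The documents give no IV disposition, so a model has to be assumed: one compartment, 15-min infusion, k = ln 2 / half-life. The half-lives are 1.5, 3 and 5.2 h; the end values are the range of fed oral means in Protocol 2.2.2.2. True Cmax is at 15 min. Ratios of observed to true Cmax, in order of half-life:

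- Ordinary practice, normal timing error with SD 1 min (assumed) on all samples to 60 min, 4,000 simulated draws: 0.974, 0.979, 0.986, which is 2.6, 2.1 and 1.4% low. The written window does not enter this calculation.
- 15-min sample at the IV-clock edges. Late by 1.5 min, exp(−k × 1.5/60) = 0.989, 0.994, 0.997. Early by 1.5 min, the larger of C(13.5)/C(15) and the 30-min sample = 0.905, 0.944, 0.967.
- 5-min sample drawn at its oral-clock late edge of 23.5 min, the 10- and 15-min samples later still: exp(−k × 8.5/60) = 0.937, 0.968, 0.981, with Tmax 23.5 min.
- Only the 15-min sample at an oral-clock edge, so that the 30-min sample supplies Cmax: exp(−k × 15/60) = 0.891, 0.944, 0.967, with Tmax 30 min. This puts the 15-min sample at −4.5 min, before the 5-min one, or at 34.5 min, after the 30-min one.

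**5. What the choice of clock does change.** With the same SD of 1 min, the chance of exceeding the IV-clock window is P(|Z| > 0.5) = 0.62 at 5 min, P(|Z| > 1.0) = 0.32 at 10 min and P(|Z| > 1.5) = 0.13 at 15 min. On the oral clock it is effectively zero. The concentrations are the same in both cases; only the deviation log differs.

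**The case for a change.** The strongest point is that a logging rule which does not name its clock cannot be applied consistently, and that the two readings differ 37-fold at 5 min (18.5/0.5) and 13-fold at 15 min (19.5/1.5). That stands as a criticism of the wording.

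It can also be said that drug leaving plasma quickly would make the stakes larger. With an assumed distribution half-life of 10 to 15 min and a fast coefficient of 50 to 80%, the case with the 5-min sample at 23.5 min gives Cmax 15 to 34% low. If all three early samples sit at the oral-clock limits, assumed one- and two-compartment profiles give AUCinf at 0.81 to 0.99 of its true value even with actual times. These figures are arithmetically right, but they need staff to miss all three early samples by more than 18 minutes despite the instruction to aim for exact time. With only the 15-min sample 19.5 min late, AUCinf is 0.965 to 1.006 of true. They show what the loosest reading would tolerate, not what is likely to happen.

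Finally, the infusion lasts only approximately 15 minutes, and no sentence ties the 15-min draw to its actual end. Protocol 6.1.1 does call for a calibrated syringe pump over 15 minutes, and the infusion row of the Schedule of Activities appears to end in the 15-minute column, although that table is broken in the available copy. Finer instructions are deferred to the laboratory manual and site administration instructions, which are not available here.

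**Conclusion.** No change follows. This is a loosely worded clause that a site and a pharmacokineticist can be expected to read sensibly, and a wider or narrower window does not alter the planned results. Exact nominal time remains the target. Actual times, taken from the start of infusion for IV data, are used for the parameters (Protocol 9.4.2.1.1). The SAP lists departures from nominal time without reference to any window (8.2.3.3.2) and lets the pharmacokineticist exclude a value whose timing is of concern (5.8).

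Under the one-compartment assumption with SD 1 min, mean IV Cmax is 1.4 to 2.6% low on either clock, in a descriptive secondary endpoint of a study that tests no hypothesis. No material effect on IV AUC, CL, Vss or F is shown under realistic timing, and Fa rests on urine. What remains is how many minor timing departures are recorded as deviations.

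Tightening the text would bring no reliable gain. A rule that the 15-min sample be taken only after the infusion ends would not clearly help: on the fast-distribution profiles above, a sample 2 min after the end is already 4 to 10% low. The conclusion rests on ordinary timing discipline in an inpatient unit. It would weaken only if a site actually worked to the oral-clock limits for the first three IV samples.
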